6.2.3.1 Implementation of Dose Escalation Decisions

To implement dose escalation decisions, the available toxicity information (including adverse events and laboratory abnormalities that are not DLTs), and/or the available PK and PD information will all be evaluated by the investigators and Haihe clinical study personnel (including

the study physician and statistician) during a dose decision meeting by teleconference. Drug administration at the next higher dose level may not proceed until the investigator receives written confirmation from Haihe indicating that the results of the previous dose level were evaluated and that it is permissible to proceed to a higher dose level.

6.2.3.2 Dose cohort modification

Provisional dose level cohorts are listed in [Table 6-4](#). Possible changes in dose administration according to the BOIN include but are not limited to:

- Enrollment of a new cohort to the current dose level;
- Enrollment of a new cohort to a dose below the starting dose for the study;
- Enrollment of a new cohort to an intermediate dose between the current and preceding dose;
- Enrollment of a new cohort to an intermediate dose between the current and the next planned dose;
- Termination of any further escalation of study drug.

6.2.3.3 Intra-Patient dose escalation

Intra-patient dose escalation is not permitted at any time with the first four cycles of treatment.

After the first four cycle is completed, individual patients may be considered for treatment at a dose of HH2710 higher than the dose to which they were initially assigned. In order for a patient to be treated at a higher dose of HH2710, he or she must have tolerated the lower dose for at least two cycles of therapy (i.e. he or she must not have experienced any HH2710-related toxicity CTCAE grade ≥ 2 at the lower dose originally assigned). Moreover, the new, higher dose with which the patient is to be treated must be a dose that has completed DLT evaluation and has not exceeded the maximum tolerated dose (MTD). There is no limit to the number of times a patient may have his or her dose of HH2710 increased. For any further increase after the initial intra-patient dose escalation, the following rules apply: the patient must have experienced no CTCAE grade ≥ 2 , HH2710-related toxicity over at least two cycles of therapy at the lower dose, and the higher dose being considered must have been fully DLT evaluated and shown not to exceed the MTD. Consultation and agreement with Haihe must occur prior to any intra-patient dose escalation occurring. These changes must be recorded on the Dosage Administration Record eCRF. Data from the first cycle of treatment at the new dose level will not be formally included into the statistical model describing the relationship between dose and occurrence of DLT. However, this data will be incorporated into the clinical assessment of safety within a dose escalation teleconference.

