Other assessments	
– Plasma PK parameters;– Pharmacodynamics assessment on pre- and post-treatment newly obtained tumor samples and peripheral blood mononuclear cells (PBMCs);– The correlation between biomarkers and the response of HH2710.
Data analysis	
The study data will be analyzed and reported based on all patients' in Phase I and Phase II up to the time when all patients have completed at least one cycle of treatment or discontinued the study.
 
The study is descriptive in nature and is not designed to provide definitive results regarding antitumor activity. Descriptive statistics will be used to summarize all baseline patient characteristics, treatment administration, safety variables, and signs of antitumor activity.
 
All patients who receive at least one dose of HH2710 will be included in the safety analysis. Incidence of serious and non-serious AEs, including those that are dose limiting, will be tabulated by dose, system organ class, and preferred term.
 
All variables obtained at different observation time points will be statistically described according to the dose cohorts, unless a statistical description of certain time points is not specified in the study protocol. In general, descriptive variables are statistically described using number of observations, mean, median, standard deviation, minimum and maximum values, Q1 and Q3 values, while categorical variables use different frequency types and their relative percentages. A safety analysis of DLT and adverse events, as well as other safety indicators for HH2710, will be performed to guide dose escalation. The final analysis of the study will be based on data collected throughout the study.
 
The sample size for Phase I of this study was determined by clinical considerations. A maximum sample size is 58 patients for the dose escalation (ATD + BOPIN) to assess dose limiting toxicities (DLT), maximum tolerated dose (MTD), and the recommended Phase 2 dose (RP2D).
 
For Phase I expansion, additional up to 15 patients per cohort may be included in order to further evaluate the safety, PK and anti-tumor activity among biomarker-selected patients. One or more dose levels and dosing frequencies (QD, or BID) may be expanded based on the available data. Patients enrolled could have different tumor types with specific MAPK pathway genetic alteration information. The total number of patients will depend upon the number of dose expansions necessary.

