Patients with different cancer types enrolled in the dose expansion stage must have confirmation of specific MAPK pathway genetic alteration. During the study, the sponsor and investigators may request one or several dose levels and different dose regimens (QD, or BID) cohorts to further explore more PK and PD data. Such requests will be discussed with the investigator(s), sponsor and medical monitor(s), and should be based on all data available at that time, including safety and clinical activity, determinations of pharmacokinetics, pharmacodynamics, and cumulative toxicity. There are no specific stopping criteria for this part of the study, however, emerging data from the expansion phase will be monitored regularly by the data review committee.

MTD estimation:

After the escalation is completed, select the MTD based on the isotonic regression as specified in [64]. Specifically, select the MTD for which the isotonic estimate of the toxicity rate is closest to the target toxicity rate. If there are ties, select the higher dose level when the isotonic estimate is lower than the target toxicity rate and select the lower dose level when the isotonic estimate is greater than or equal to the target toxicity rate.

Biologically Effective Dose (BED)

The Biologically Effective Dose (BED) is the dose chosen by the sponsor and is based on all available preclinical data and clinical safety, efficacy, PK, and PD data.

Definition of RP2D

The RP2D is defined as the dose level chosen by the sponsor (in consultation with the investigators) for the dose extension in Phase II, based on safety, tolerability, efficacy, PK, and PD data collected during the dose escalation stage and/or phase I dose expansion of the study. RP2D maybe adjust if not suitable.

Determination of RP2D

Prior to beginning the phase II stage, there will be a comprehensive review of all safety, PK, and/or PD data from cycle 1 and subsequent cycles of phase I dose escalation and expansion to determine the risk/benefit profile of the MTD. Based on this review, the phase II stage will begin at the MTD/RP2D if the MTD is tolerated. The dose studied in phase II stage, MTD/RP2D, is defined as final recommended dose.

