8.1 General Principles

TFLs will be displayed by treatment groups, which are the dose levels for phase I study and cohort levels for phase II study. If necessary, the same dose level may be combined and analyzed across phase I and II studies.

Continuous variables will be summarized using the following descriptive summary statistics: the number of subjects (n), mean, standard deviation (SD), median, minimum value (min), and maximum value (max). The number of subjects (n) will represent the number with non-missing data on the continuous variable under consideration. The precision of the measurement for each continuous variable will be used to determine the number of decimal places to present in tables, figures, and derived listings. Unless otherwise specified, min and max values will be reported with the same decimal as the units of measure; the mean, median will be reported to 1 greater decimal place, the SD will be reported to 2 greater decimal place, all of them will not be greater than 4 decimal place. Any values that require transformation to standard units (metric or International System [SI]) will be converted with the appropriate corresponding precision.

Categorical variables will be summarized using counts and percentages (95% confidence interval of percentage if necessary). Percentages will be presented to 1 decimal place unless otherwise specified.

Treatment group indicates the dose level of HH2710 (such as 25 mg BID) and total (if more than one dose level) for phase I and cohort in Phase II.

Baseline value, unless otherwise specified, will be defined as the last non-missing measurement (scheduled or unscheduled) collected prior to the initial administration of study drug. For example, if an assessment was performed at screening and Day 1 prior to initial dosing of study drug, then Baseline is the Day 1 measurement if the Day 1 value is not missing; if the Day 1 value is missing, then the screening value is Baseline, and so forth.

Change (absolute change) from baseline will be calculated as post-baseline value - baseline value.

Unscheduled visits: Subject data for safety or efficacy assessments (such as unscheduled labs) will be incorporated into the cycle windows appropriate to the scheduled visits. For summary by visit tables and figures, only scheduled visits will be included in the analysis.

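### Patients' doses may be raised after cycle 4, but the by-dose Phase I safety tables have no cut at escalation, so later events fall by default in the originally assigned dose row

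*Protocol*

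**What the plan says.** Protocol 6.2.3.3 sets the timing: "Intra-patient dose escalation is not permitted at any time with the first four cycles of treatment". After that, "individual patients may be considered for treatment at a dose of HH2710 higher than the dose to which they were initially assigned", and "There is no limit to the number of times a patient may have his or her dose of HH2710 increased". Each increase is conditional. The patient must have tolerated the lower dose for at least two cycles, which the protocol explains as "he or she must not have experienced any HH2710-related toxicity CTCAE grade" 2 or higher at the dose originally assigned. The new dose "must be a dose that has completed DLT evaluation and has not exceeded the maximum tolerated dose (MTD"), and the sponsor must agree. Dose changes go on the Dosage Administration Record eCRF. The section gives one rule for the resulting data: the first cycle at the new dose stays out of the formal dose-DLT model but is considered at the dose-escalation teleconference.

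On reporting, the Data analysis entry of the Protocol summary says that AE incidence "will be tabulated by dose, system organ class, and preferred term", and that all variables are described by dose cohort. The Glossary defines a cohort as newly enrolled patients at one dose and regimen, and equates this with a treatment group. SAP 8.1 says: "Treatment group indicates the dose level of HH2710 (such as 25 mg BID) and total (if more than one dose level") in Phase I. SAP 8.8.1.1 counts TEAEs from first dose to the safety follow-up. SAP 8.8.1.3, 8.8.1.4 and 8.8.1.6 add shift tables to the worst post-baseline finding. SAP 8.6 summarises dose reductions, interruptions and withdrawals, but not increases.

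For RP2D selection, Protocol 6.2.3 says "there will be a comprehensive review of all safety, PK, and/or PD data from cycle 1 and subsequent cycles" of the escalation and expansion stages.

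**The concern.** AE incidence, type and severity form a Phase I primary endpoint, and they are read by dose. If a patient's dose rises but the patient stays in the enrolment row, whatever happens at the higher dose is reported under the lower one. The lower-dose row then looks more toxic than that dose is, and the experience at the higher dose is not shown there. Both effects tend to flatten the apparent relation between dose and toxicity.

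The protocol recognises that post-escalation data differ from ordinary cohort data, because it keeps the first cycle at the new dose out of the DLT model. That separation is not carried into the TEAE or worst-post-baseline tables. These tables cover the later cycles that the RP2D review is meant to consider.

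**Working it through.** The plan gives no figure on this point to reproduce. The check compares the definitions and then sizes one carried-over event.

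**1. Where a post-escalation event goes.**
- The row is fixed at enrolment: the Glossary's cohort is newly enrolled patients at a given dose, and the Protocol summary describes all variables by dose cohort. SAP 8.1 speaks of dose level without saying assigned, actual or at onset.
- The window stays open: SAP 8.8.1.1 runs to the safety follow-up with no stop at a dose increase.
- Nothing else reassigns the event: SAP 8.12 (changes from the protocol) and the censoring tables in SAP Appendices A to C do not mention dose increases.
- Result: with one row per patient and no cut, the event is counted under the assigned dose. This follows by default from the definitions; no sentence states it as a rule.

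**2. What is outside the problem.**
- The DLT window is 21 days (Protocol 2.3). The earliest increase comes after 4 × 21 = 84 days. The first cycle at a new dose is excluded from the DLT model, so DLT and MTD estimation is untouched.
- The serial post-dose ECGs are on C1D1 and C2D1 (Protocol 7.2.1.7), before any increase. By-visit summaries through cycle 4 are also unaffected.
- Phase II tables are grouped by tumour cohort (SAP 8.1), so this is mainly a Phase I matter.

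**3. Size of one carried-over event.** At 18 Jan 2022 the escalation groups had 3, 3, 4, 4, 4 and 4 patients (Protocol 4.1). The rate is x/n, with exact Clopper-Pearson 95% limits:

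| Group size | No event | One carried-over event |
|---|---|---|
| 3 | 0/3 = 0% (0 to 70.8%) | 1/3 = 33.3% (0.8 to 90.6%) |
| 4 | 0/4 = 0% (0 to 60.2%) | 1/4 = 25.0% (0.6 to 80.6%) |

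The shift is 25 to 33 percentage points. In a group filled to the Part A limit of 15 it would be 1/15 = 6.7 points.

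**4. Would the exposure table reveal it?** SAP 8.6 defines relative dose intensity as (cumulative dose / actual weeks) / (planned dose / planned weeks). Assume that the planned dose stays at the assigned daily dose a, with four uninterrupted cycles at a and four at a higher daily dose b. The ratio is then (a + b) / 2a:
- 50 to 100 mg/day: 150/100 = 150%
- 200 to 300 mg/day: 500/400 = 125%
- 300 to 400 mg/day: 700/600 = 117%

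The category above 120% would catch the first two and miss the third. It would reassign no events in any case.

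**5. Responses.** Scans are at C3D1 and every two cycles thereafter, with confirmation about six weeks later (Protocol 7.2.5). C5D1 is day 4 × 21 + 1 = 85 and C7D1 is day 6 × 21 + 1 = 127, which is 42 days apart. A response first seen at C5D1, before an increase, could therefore be confirmed at C7D1, after it. A cut that kept only pre-escalation scans would discard that response although it arose at the assigned dose.

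**The case against.** The strongest reply is that no sentence assigns these events to the lower dose. The SAP says only dose level, and Protocol 10.6.6 requires a listing of all events with start and end times. With the eCRF dosing record, dose at onset can be recovered. RP2D comes from a broad review and is not read mechanically from tables. All of this is true. It makes the problem repairable, but it does not supply the missing rule, and the Glossary and Protocol summary point to enrolment-dose rows.

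A reader might infer several stronger things that the documents do not support:

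- *That every related Grade 2 or higher event in an escalated patient is mislabelled.* This needs the tolerance condition to cover all time at the assigned dose. It can also be read as covering only the qualifying two cycles. A patient with a Grade 2 event in cycle 1 and clean later cycles could then escalate, and that event would correctly belong to the lower dose.
- *That low doses will be credited with responses.* Phase I efficacy is exploratory, and SAP 8.7.1.4 sends any such analysis to separate documents. The point applies only if by-dose response tables are produced.
- *That the eye toxicity at 600 and 800 mg is being blurred.* Those events are already reported under those doses, and nothing shows that any was displaced.
- *That escalation has no ceiling.* The number of increases is unlimited, but each is conditional and may not exceed the MTD.

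SAP 7 says that the programme has stopped and that many planned analyses may not be run. This lowers the consequence for RP2D selection, but any by-dose Phase I safety table that is produced still needs the rule.

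**Conclusion.** The point holds as a gap in the by-dose Phase I safety analysis. As written, TEAEs and worst post-baseline laboratory, vital-sign and ECG findings that arise after an intra-patient increase fall by default in the originally assigned dose row. One such event moves a group of three or four from 0% to 33% or 25%.

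This assumes one row per patient, fixed at enrolment, and at least one escalated patient with such an event. The number escalated is not given, so the realised effect may be nil. A reader might infer that the MTD is biased; it is not, for the reasons of timing and exclusion shown in the working. The change should be made because it is cheap and concerns a primary endpoint.

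**What to change.** - **SAP 8.1:** define the Phase I treatment group as the initially assigned dose.
- **SAP 8.8:** cut by-dose TEAE and worst-post-baseline summaries at the first escalated dose. Show later events in a separate column, *after intra-patient escalation*, and add dose at onset to the listings.
- **SAP 8.6:** summarise the number and timing of dose increases. If nobody was escalated, one sentence saying so closes the point.
- **Any by-dose Phase I BOR or ORR:** keep a response first documented before escalation under the assigned dose, even if it is confirmed afterwards. Flag and list responses first documented after escalation, with the dose at response.

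The dates are already on the Dosage Administration Record eCRF, so the cost is SAP wording and modest programming. There are two small downsides. An escalated patient can appear in two columns, so columns need not sum to the number of patients. The post-escalation column also contains patients selected for tolerance, so it should not be pooled with the higher-dose cohorts; doing so could dilute their toxicity rates. Nothing here changes the escalation rules themselves.

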6.2.4 Definitions of dose limiting toxicities (DLTs)

DLT is defined as: any toxicity meeting the specified criteria and considered at least possibly related to HH2710 (i.e., any toxicity for which a clear alternative etiology such as disease

progression has not been identified) should be considered a DLT per National Cancer Institute Common Terminology Criteria for Adverse events (NCI-CTCAE V5.0) standard, which met any of the following, NCI-CTCAE V5.0 will be used for all grading, and compliance of 80% (i.e. 17 of 21 days) in Cycle 1 is required for a patient to be included in the DLT evaluation. For the purpose of dose-escalation decisions, DLTs will be considered and included in the BOIN. The criteria for defining dose-limiting toxicities see Table 6-6.

Table 6-6 Criteria for defining dose-limiting toxicities

TOXICITY	DLT CRITERIA
Blood and lymphatic system disorders	
≥ Grade 4 hematologic toxicity
 
Grade 3 thrombocytopenia with bleeding or with requirement of transfusion of platelets
 
Any grade febrile neutropenia
 
Note: Given the high frequency of events related to underlying disease in subjects of LCH, the investigator should confirm the causality of these events before judgement of DLTs, based on severity or duration is longer than that expected with standard-of-care treatment or other clinical evidence

Cardiac disorders	
Asymptomatic decrease of LVEF > 10% compared to baseline and the LVEF is below the institution's LLN b.
 
Left ventricular systolic dysfunction CTCAE Grade ≥ 3
 
Other cardiac disorders CTCAE Grade ≥ 3

Vascular disorders Hypertension	Persistent hypertension CTCAE Grade ≥ 3 requiring more than one drug or more intensive therapy than previously administered.
General disorders and administration site conditions	Fatigue CTCAE Grade 3 for > 72 hours
Skin and subcutaneous tissue disorders: Rash and/or photosensitivity	Rash/photosensitivity CTCAE Grade 3 for > 72 hours despite skin toxicity treatment, photosensitivity Grade 4
Eye disorders	Any grade of retinal vein occlusion (RVO)
Gastrointestinal disorders	
Diarrhea CTCAE Grade 3 > 72 hrs., despite the use of anti-diarrhea therapy; Diarrhea Grade 4
 
Nausea/ vomiting CTCAE Grade 3 > 72 hrs., despite the use of anti-emetic therapy; Vomiting Grade 4

TOXICITY	DLT CRITERIA
	Pancreatitis CTCAE Grade ≥ 3
Investigations ^a	
	Blood bilirubin CTCAE Grade ≥ 3
	ALT/AST > 3 ULN and concomitant TBL > 2 ULN in the absence of evidence of biliary obstruction (i.e., significant elevation of ALP) or some other explanation of the injury (e.g., viral hepatitis, alcohol hepatitis) of any duration (i.e. Hy's law)
	AST or ALT CTCAE Grade 3 for > 72 hours
	AST or ALT CTCAE Grade 4
	Serum alkaline phosphatase CTCAE Grade 3
	Serum lipase and/or serum amylase (asymptomatic) CTCAE Grade 3 > 72 hours
	Serum lipase and/or serum amylase CTCAE Grade 4
	Serum creatinine CTCAE Grade ≥ 3
	Serum CK/CPK CTCAE Grade 3 for > 72 hours
	Serum CK/CPK CTCAE Grade 4
	Neutrophil count CTCAE Grade 3 for > 72 hours
	Neutrophil count CTCAE Grade 4
	Platelet count CTCAE Grade 3 with signs of bleeding
	Platelet count CTCAE Grade 4
	ECG QTc interval prolonged CTCAE \geq Grade 3
	Electrolyte imbalance Grade 4; Asymptomatic electrolyte imbalance Grade 3 > 72 hours
Other hematologic & non-hematologic toxicities	Any other CTCAE Grade ≥ 3 toxicity except: Lymphocyte count decreased (lymphopenia) CTCAE Grade ≥ 3 unless clinically significant
	Other clinically significant/unacceptable toxic events not listed, judged by the SMC as DLT;

TOXICITY	DLT CRITERIA
All AEs of the specified grade and toxicity must be considered a DLT if they cannot definitively be attributed to disease progression or other extraneous cause.	

^a For any CTCAE Grade 3 or 4 hepatic toxicity that does not resolve within 7 days to CTCAE Grade ≤ 1 (or CTCAE Grade ≤ 2 if liver infiltration with tumor present), an abdominal CT scan must be performed to assess if it is related to disease progression.
	

CTCAE V5.0 will be used for all grading.
	

Patients may receive supportive care (e.g. Packed red blood cells) as per local institutional guidelines.
	

G-CSF may be used to treat patients who have developed dose-limiting neutropenia, as per institutional guidelines, following discontinuation of HH2710 treatment. Optimal therapy for vomiting or diarrhea will be based in institutional guidelines, with consideration of the prohibited medications listed in this protocol. Grade 3 laboratory investigations other than serum creatinine, bilirubin, AST or ALT will not be considered a DLT unless they are associated with clinical manifestations and judged by the SMC.
	

For the exceptions provided, the Grade 3 AEs should resolve to \leq Grade 1 within 72 hours
	

In order to define DLT, patients should not be prophylactically prescribed antiallergic drugs support, antiemetics, antidiarrheals, or antipyretics. If a patient experiences grade 2 or greater nausea, diarrhea, vomiting, and/or skin lesion, medical intervention should occur.

The investigator must notify the Sponsor immediately of any unexpected CTCAE grade ≥ 3 adverse events or laboratory abnormalities. Prior to enrolling patients into a higher dose level, CTCAE grade ≥ 2 adverse events will be reviewed for all patients at the current dose level.

The study will set up a Safety Monitoring Committee (SMC) to oversee safety, dose escalation decisions, MTD or BED, recommended doses for Phase II, determination of RP2D, and other key research decisions. At each dose level (DL), the SMC will determine the number of patients enrolled in the next DL, the dose increase, and the frequency of the most appropriate use based on all available PK and safety data (once daily [QD] or twice daily [BID]). However, if the sponsor's opinion differs from SMC, the decision process will be described in the SMC charter. SMC members include at least the main investigator, a PK expert, a drug safety physician, and a medical monitor. The investigator will continue to monitor the safety of all patients until the end of the safety follow-up visit (SFUV).

